**P15-743 (HCV RWE)\_ STATISTICAL ANALYSIS PLAN \_ final 2.0 \_ 02 Feb 2018**

AbbVie LLC

P15-743 (HCV RWE)

**Table 4.4.1 Adverse events by severity**

The safety population

Page X of X

| System Organ Class (SOC)
Preferred term (PT) | Severity | ABBVIE REGIMEN + RBV           |                                | ABBVIE REGIMEN - RBV           |                                | Overall
N=XX
n (%) /E |
|---|----------|--------------------------------|--------------------------------|--------------------------------|--------------------------------|-----------------------------|
|   |          | 12 weeks
(N=XX)
n (%) /E | 12 weeks
(N=XX)
n (%) /E | 12 weeks
(N=XX)
n (%) /E | 12 weeks
(N=XX)
n (%) /E |                             |
| Total [1]                                       | Severe   | XX (XX.X) /XX                  | XX (XX.X) /XX                  | XX (XX.X) /XX                  | XX (XX.X) /XX                  | XX (XX.X) /XX               |
|   | Moderate | XX (XX.X) /XX                  | XX (XX.X) /XX                  | XX (XX.X) /XX                  | XX (XX.X) /XX                  | XX (XX.X) /XX               |
|   | Mild     |                                |                                |                                |                                |                             |
|   | Total    | XX (XX.X) /XX                  | XX (XX.X) /XX                  | XX (XX.X) /XX                  | XX (XX.X) /XX                  | XX (XX.X) /XX               |
| System Organ Class 1                            | Severe   | XX (XX.X) /XX                  | XX (XX.X) /XX                  | XX (XX.X) /XX                  | XX (XX.X) /XX                  | XX (XX.X) /XX               |
|   | Moderate | XX (XX.X) /XX                  | XX (XX.X) /XX                  | XX (XX.X) /XX                  | XX (XX.X) /XX                  | XX (XX.X) /XX               |
|   | Mild     |                                |                                |                                |                                |                             |
|   | Total    | XX (XX.X) /XX                  | XX (XX.X) /XX                  | XX (XX.X) /XX                  | XX (XX.X) /XX                  | XX (XX.X) /XX               |
| Preferred term A                                | Severe   | XX (XX.X) /XX                  | XX (XX.X) /XX                  | XX (XX.X) /XX                  | XX (XX.X) /XX                  | XX (XX.X) /XX               |
|   | Moderate | XX (XX.X) /XX                  | XX (XX.X) /XX                  | XX (XX.X) /XX                  | XX (XX.X) /XX                  | XX (XX.X) /XX               |
|   | Mild     |                                |                                |                                |                                |                             |
|   | Total    | XX (XX.X) /XX                  | XX (XX.X) /XX                  | XX (XX.X) /XX                  | XX (XX.X) /XX                  | XX (XX.X) /XX               |
| Preferred term B                                | Severe   | XX (XX.X) /XX                  | XX (XX.X) /XX                  | XX (XX.X) /XX                  | XX (XX.X) /XX                  | XX (XX.X) /XX               |
|   | Moderate | XX (XX.X) /XX                  | XX (XX.X) /XX                  | XX (XX.X) /XX                  | XX (XX.X) /XX                  | XX (XX.X) /XX               |
|   | Mild     |                                |                                |                                |                                |                             |
|   | Total    | XX (XX.X) /XX                  | XX (XX.X) /XX                  | XX (XX.X) /XX                  | XX (XX.X) /XX                  | XX (XX.X) /XX               |
| ...   | ...      | ...                            | ...                            | ...                            | ...                            | ...                         |
| System Organ Class 2                            | Severe   | XX (XX.X) /XX                  | XX (XX.X) /XX                  | XX (XX.X) /XX                  | XX (XX.X) /XX                  | XX (XX.X) /XX               |
|   | Moderate | XX (XX.X) /XX                  | XX (XX.X) /XX                  | XX (XX.X) /XX                  | XX (XX.X) /XX                  | XX (XX.X) /XX               |
|   | Mild     |                                |                                |                                |                                |                             |

**P15-743 (HCV RWE) \_ STATISTICAL ANALYSIS PLAN \_ final 2.0 \_ 02 Feb 2018**

| System Organ Class (SOC)
Preferred term (PT) | ABBVIE REGIMEN + RBV           |              | ABBVIE REGIMEN - RBV           |              | Overall
N=XX
n (%) /E |
|---|--------------------------------|--------------|--------------------------------|--------------|-----------------------------|
|   | 12 weeks
(N=XX)
n (%) /E | XX(XX.X) /XX | 12 weeks
(N=XX)
n (%) /E | XX(XX.X) /XX |                             |
| Severity  |                                |              |                                |              | ...                         |
| Total   | XX(XX.X) /XX                   | XX(XX.X) /XX | XX(XX.X) /XX                   | XX(XX.X) /XX | XX(XX.X) /XX                |
| ...   | ...                            | ...          | ...                            | ...          | ...                         |
| ...   | ...                            | ...          | ...                            | ...          | ...                         |

N: the number of patients in the safety population.  
n: the number of patients who have AE with appropriate SOC/PT. Percentages are calculated as (100 x n/N) .  
E: the number of AE episodes, which have an appropriate SOC and/or PT.  
Each SOC/PT category includes only AEs with the highest severity in each patient. Each patient is counted only once in the Total lines and in the lines for each SOC or SOC/PT categories. Thus, if patient has several AEs with the same SOC and PT but different severity, only the AEs with maximum severity will be accounted, while each patient will be accounted only once in line which corresponds the highest severity of his AEs.  
[1] The Total lines displays the number (n) and the proportion (%) of patients who have AEs. Each patient is counted once in line which corresponds the highest severity of all his AEs. #E displays the number of all AEs episodes with appropriate severity in the study.  
The coding is carried out by the dictionary MedDRA v.20.1.  
The table does not include AEs that occurred prior to the first intake of the study drug.  
The data is sorted alphabetically: first by SOC, then by PT and relationship to the drug.

Program code, date, time Data extracted: DD.MM.YYYY

Similar to table 4.4.1, table 4.4.2 will be constructed:

**Table 4.4.2 Serious adverse events by severity**

**P15-743 (HCV RWE) \_ STATISTICAL ANALYSIS PLAN \_ final 2.0 \_ 02 Feb 2018**

**Hematology**

AbbVie LLC  
P15-743 (HCV RWE)  
**Table 4.5.1 Hematology. Descriptive statistics**  
The safety population  
Page X of X

| Parameter
Visit
Statistics | Test result                                  |  | Change from baseline                         |  |
|----------------------------------|--|--|--|--|
|                                  | ABBVIE REGIMEN
+ RBV 12 weeks
(N = XX) | ABBVIE REGIMEN
- RBV 12 weeks
(N = XX) | ABBVIE REGIMEN
+ RBV 12 weeks
(N = XX) | ABBVIE REGIMEN
- RBV 12 weeks
(N = XX) |
| Overall
(N = XX)              | ...  | ...  | ...  | ...  |
| Overall
(N = XX)              | XX   | XX   | XX   | XX   |
| Mean                             | XX.X   | XX.X   | XX.X   | XX.X   |
| SD                               | XX.XX  | XX.XX  | XX.XX  | XX.XX  |
| Median                           | XX.X   | XX.X   | XX.X   | XX.X   |
| IQR                              | XX.X   | XX.X   | XX.X   | XX.X   |
| Min                              | XX   | XX   | XX   | XX   |
| Max                              | XX   | XX   | XX   | XX   |
| EoT                              | XX   | XX   | XX   | XX   |
| n                                | XX.X   | XX.X   | XX.X   | XX.X   |
| Mean                             | XX.X   | XX.X   | XX.X   | XX.X   |
| SD                               | XX.XX  | XX.XX  | XX.XX  | XX.XX  |
| Median                           | XX.X   | XX.X   | XX.X   | XX.X   |
| IQR                              | XX.X   | XX.X   | XX.X   | XX.X   |
| Min                              | XX   | XX   | XX   | XX   |
| Max                              | XX   | XX   | XX   | XX   |
| SVR12                            | XX   | XX   | XX   | XX   |
| n                                | XX.X   | XX.X   | XX.X   | XX.X   |
| Mean                             | XX.X   | XX.X   | XX.X   | XX.X   |
| SD                               | XX.XX  | XX.XX  | XX.XX  | XX.XX  |
| Median                           | XX.X   | XX.X   | XX.X   | XX.X   |
| IQR                              | XX.X   | XX.X   | XX.X   | XX.X   |
| Min                              | XX   | XX   | XX   | XX   |
| Max                              | XX   | XX   | XX   | XX   |
| SVR24                            | XX   | XX   | XX   | XX   |
| n                                | XX.X   | XX.X   | XX.X   | XX.X   |
| Mean                             | XX.X   | XX.X   | XX.X   | XX.X   |
| Overall
(N = XX)              | ...  | ...  | ...  | ...  |

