The ABBVIE REGIMEN has been studied with and without RBV in over 2,300 patients in Phase III trials across a variety of patient populations including those with compensated cirrhosis. Based on Phase III data, the ABBVIE REGIMEN, with or without RBV, was well tolerated with a low discontinuation rate. Adverse events (AEs) were typically mild, and many of the AEs and laboratory abnormalities reported were attributable to the presence of RBV. However, these AEs were much milder than observed when RBV was given in combination with interferon. Transient, asymptomatic serum alanine aminotransferase (ALT) elevations were observed at a low rate, were not associated with hepatic dysfunction and generally resolved with ongoing treatment. A disproportionate number of the cases were in women on concurrent ethinyl estradiol-containing therapy (i.e., contraceptives or hormone replacement) and discontinuation of the hormonal therapy with continuation or brief interruption of the ABBVIE REGIMEN led to resolution in serum ALT elevation. Transient elevations in serum bilirubin (predominantly indirect) were observed in subjects receiving the ABBVIE REGIMEN with RBV, related to the inhibition of the bilirubin transporters, organic anion-transporting polypeptides (OATPs) 1B1/1B3, by paritaprevir and RBV-induced hemolysis. Bilirubin elevations occurred after initiation of treatment, peaked by study Week 1, and generally resolved with ongoing therapy. Bilirubin elevations were not associated with aminotransferase elevations. The frequency of indirect bilirubin elevations was lower among subjects who did not receive RBV.

Response of CHC genotype 4 was assessed in the phase II study PEARL-I in which 86 treatment-naïve patients were randomized to the 2 DAA combination of Paritaprevir/r – ombitasvir with vs. without RBV for 12 weeks. The SVR was 100% with RBV vs. 91% without RBV [61]. No serious SAEs or AEs leading to discontinuation were reported.

These results from pivotal studies are encouraging and the new interferon-free regimens might provide physicians with the armamentarium to cure the vast majority of patients

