9.7.4 Clinical Laboratory Data

All reported clinical laboratory test results will be assigned to one of the time points using the time windows specified in the table below.

Table 4 - Analysis Time Windows

Phase	Time point	Time Window
Pre-Treatment	Baseline	Last value prior to start of study treatment (i.e. \leq study day 1)
Treatment Weeks		Study day during treatment period (Study day 1 = first treatment day)
	4 (day 29)	15 – 42
	8 (day 57)	43 – 70
	12 (day 85)	71 – 98
	16 (day 113)	99 – 126
EoT	Actual EoT	Study day of last dose (28 days prior to EoT - 14 days post EoT)
Post Treatment	4 weeks (day 29 post EoT)	15 – 56 post EoT
	12 weeks (day 85 post EoT)	57 – 112 post EoT
	24 weeks (day 169 post EoT)	141 – 196 post EoT

Mean changes from baseline to each post-baseline visit will be summarized descriptively.

Laboratory data values collected during the treatment period will be categorized as low, normal, or high based on reference ranges used in this study. The number and percent of patients who experience post-baseline shifts during treatment in clinical laboratory values from low/normal to high and high/normal to low based on the reference range will be summarized.

Additional details of the analyses of clinical laboratory data will be specified in the SAP.

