### **5.2 Windowing conventions**

Due to exploratory nature of the study all interim time-points will be separated into visits in the analysis stage. The most detailed possible situation is:

- on-treatment Week 4 from 15 to 42 study days;
- on-treatment Week 8 from 43 to 70 study days;
- on-treatment Week 12 from 71 to 98 study days;
- on-treatment Week 16 from 99 to 126 study days;
- post-treatment Week 4 from 15 to 56 days post EoT.

Table 5.1 describes assignment of time point windows to the following data for purposes of effectiveness, safety and tolerability analyses.

Table 5.1 – Analysis time windows

| Time point             | Time Window  |                        |
|------------------------|--|------------------------|
|                        | 12 weeks treatment   | 24 weeks treatment     |
| Baseline        | Last value prior to start of study treatment (i.e. $\leq$ study day 1) |                        |
| EoT | Last value between   |                        |
|                        | 56 and 98 study days   | 140 and 182 study days |
| SVR12           | Last value between 57 and 112 days post the study day of last dose     |                        |
| SVR24           | Last value between 141 and 196 days post the study day of last dose    |                        |

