### **11.4 Clinical Laboratory Evaluations**

Clinical laboratory evaluations include the following parameters:

- hematology results;
- blood chemistry results.

The following parameters, which are evaluated at each study visit, will be analyzed in tables and presented in listings:

- hematology:
  - hemoglobin;
  - platelets;
  - prothrombin time (seconds);
  - prothrombin time (INR);
- blood chemistry:
  - ALT;
  - AST;
  - GGT;
  - total bilirubin;
  - alpha-1-fetoprotein;
  - albumin;
  - creatinine;
  - creatinine clearance.

The results of clinical laboratory evaluations statistical analysis will be represented in accordance with section 7.1 as the following outputs:

- tables with descriptive statistics of measurement values and changes from baseline visit;
- frequency tables of out of range and clinically significant evaluates will be presented;
- shift tables based on clinical evaluation of measurements at baseline visit.

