**Table 4.5.2 Hematology. Clinical assessments**

The safety population

Page X of X

| Parameter        | ABBVIE REGIMEN + RBV
12 weeks
(N = XX) | ABBVIE REGIMEN - RBV
12 weeks
(N = XX) | Overall
(N = XX) |
|------------------|--|--|---------------------|
| Visit            |  |  |                     |
| Value            |  |  |                     |
| Hemoglobin       |  |  |                     |
| Visit 1          |  |  |                     |
| n                | XXX  | XXX  | XXX                 |
| Normal           | XX (XX.X)                                    | XX (XX.X)                                    | XX (XX.X)           |
| Abnormal NCS     | XX (XX.X)                                    | XX (XX.X)                                    | XX (XX.X)           |
| Abnormal CS      | XX (XX.X)                                    | XX (XX.X)                                    | XX (XX.X)           |
| EoT              |  |  |                     |
| n                | XXX  | XXX  | XXX                 |
| Normal           | XX (XX.X)                                    | XX (XX.X)                                    | XX (XX.X)           |
| Abnormal NCS     | XX (XX.X)                                    | XX (XX.X)                                    | XX (XX.X)           |
| Abnormal CS      | XX (XX.X)                                    | XX (XX.X)                                    | XX (XX.X)           |
| SVR12            |  |  |                     |
| n                | XXX  | XXX  | XXX                 |
| Normal           | XX (XX.X)                                    | XX (XX.X)                                    | XX (XX.X)           |
| Abnormal NCS     | XX (XX.X)                                    | XX (XX.X)                                    | XX (XX.X)           |
| Abnormal CS      | XX (XX.X)                                    | XX (XX.X)                                    | XX (XX.X)           |
| SVR24            |  |  |                     |
| n                | XXX  | XXX  | XXX                 |
| Normal           | XX (XX.X)                                    | XX (XX.X)                                    | XX (XX.X)           |
| Abnormal NCS     | XX (XX.X)                                    | XX (XX.X)                                    | XX (XX.X)           |
| Abnormal CS      | XX (XX.X)                                    | XX (XX.X)                                    | XX (XX.X)           |

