**Table 4.5.3 Hematology. Shift table (overall)**

The safety population

Page X of X

| Parameter | Visit | Normal | Abnormal NCS | Abnormal CS | Total assessed |
|-----------|-------|--------|--------------|-------------|----------------|
| Value     |       |        |              |             |                |

Hemoglobin

Visit 1

Normal

Abnormal NCS

Abnormal CS

Total assessed

XX (XX.X)  
XX (XX.X)  
XX (XX.X)  
XX (100)

EoT

Normal

Abnormal NCS

Abnormal CS

Total assessed

XX (XX.X)  
XX (XX.X)  
XX (XX.X)  
XX (100)

SVR12

Normal

Abnormal NCS

Abnormal CS

Total assessed

XX (XX.X)  
XX (XX.X)  
XX (XX.X)  
XX (100)

SVR24

Normal

Abnormal CS

Total assessed

XX (XX.X)  
XX (XX.X)  
XX (100)

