**Blood chemistry**

Similar to tables 4.5.X, the following tables will be constructed:

- Table 4.6.1 Blood chemistry. Descriptive statistics
- Table 4.6.2 Blood chemistry. Clinical assessments
  - Table 4.6.3 Blood chemistry. Shift table
- Table 4.6.4 Blood chemistry. Shift table (ABBVIE REGIMEN + RBV 12 weeks group)
- Table 4.6.5 Blood chemistry. Shift table (ABBVIE REGIMEN - RBV 12 weeks group)
  - Table 4.6.X Blood chemistry. Shift table (...)

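### The SAP laboratory table shells omit on-treatment visits and the during-treatment shift count, and days 2–14 fall in no analysis window, so transient bilirubin and ALT elevations can be missing from the laboratory summaries

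*SAP*

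**What the plan says.** **Protocol 9.7.4** (supplied version) assigns every reported laboratory result to a time point through its Table 4. It asks for mean change from baseline at each post-baseline visit. It also asks for "The number and percent of patients who experience post-baseline shifts during treatment in clinical laboratory values from low/normal to high", and for the opposite direction, judged against reference ranges. Protocol Table 2 schedules chemistry and hematology at the on-treatment visits, where available from routine care.

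**Protocol 7.1** describes two laboratory signals for this regimen. On bilirubin: "Bilirubin elevations occurred after initiation of treatment, peaked by study Week 1, and generally resolved with ongoing therapy". ALT elevations are called transient and said generally to resolve with continued treatment; no onset time is given.

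**SAP 5.2** says interim time points will be split into visits at analysis. It lists Weeks 4, 8, 12 and 16, starting with "on-treatment Week 4 from 15 to 42 study days". **SAP 11.4** plans tables and listings for parameters evaluated at each study visit, and "shift tables based on clinical evaluation of measurements at baseline visit".

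**SAP shells.** "Table 4.5.1 Hematology. Descriptive statistics", "Table 4.5.2 Hematology. Clinical assessments" and "Table 4.5.3 Hematology. Shift table (overall" carry EoT, SVR12 and SVR24 as their only post-baseline rows. The shift shell classifies values as normal, abnormal not clinically significant, or abnormal clinically significant. For chemistry, which includes ALT, AST and bilirubin, the SAP says only: "Similar to tables 4.5.X, the following tables will be constructed".

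**SAP 16** declares the methods fully consistent with the protocol and names only the PSP regression as dropped.

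**The concern.** Tolerability is a secondary objective, and the laboratory signals that the protocol itself describes occur on treatment and then resolve. A table set that goes from baseline straight to EoT cannot show an abnormality that arose and cleared in between. If the shells are programmed as drawn, the laboratory summaries could look clean in patients who had on-treatment elevations.

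The shift analysis also changes in kind. The protocol asks how many patients moved low, normal or high at any point during treatment. The shells cross-classify single visits by clinical significance, which drops the direction of change and gives no per-patient count over the treatment period.

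**Working it through.** No sample size or error rate is involved. The check compares study days with the stated windows, first with every window and then with only those that have a row in the shells.

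**Inputs**

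| Window | Study days | Row in laboratory shells? |
|---|---|---|
| Baseline | up to day 1 | yes |
| Week 4 | 15–42 | no |
| Week 8 | 43–70 | no |
| Week 12 | 71–98 | no |
| Week 16 | 99–126 | no |
| EoT, 12-week regimen | 56–98 | yes |
| EoT, 24-week regimen | 140–182 | yes |

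The week windows are the same in Protocol Table 4 and SAP 5.2. The EoT days are from SAP Table 5.1. A footnote there ties them to core-population allocation, so I checked them against Protocol Table 4, which runs from 28 days before to 14 days after the last dose. For last doses on days 84 and 168 this gives 84 − 28 = 56 to 84 + 14 = 98, and 168 − 28 = 140 to 168 + 14 = 182. The two sources agree for completed courses.

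**1. All defined windows.** Days 2–14 are uncovered in both regimens (14 − 2 + 1 = 13 days). The 24-week regimen also has a gap at days 127–139 (13 days). Both gaps conflict with the protocol's statement that all reported results are assigned.

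**2. Shell rows only.**
- 12 weeks: days 2–55 reach no row. That is 55 − 2 + 1 = 54 of 84 days, or 64%.
- 24 weeks: days 2–139 reach no row. That is 139 − 2 + 1 = 138 of 168 days, or 82%.

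**3. Adding the Week 4, 8, 12 and 16 rows.** The uncovered days shrink to 2–14 (12 weeks), or to 2–14 and 127–139 (24 weeks). Protocol Table 4 places Week 4 at day 29, so by the same convention Week 1 ends at day 8. A bilirubin peak by Week 1, about days 2–8, still lies wholly inside the day 2–14 gap. Interim rows alone do not recover it.

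**4. Exception for early stoppers.** A day 2–14 value can fall in the protocol's EoT window if the last dose minus 28 is at most 14, that is, if the last dose is on or before day 42. SAP section 6 likewise uses the actual EoT, without windowing, for target-population patients who stop early.

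**The case against.** The strongest reply is that the SAP text already covers this. Section 5.2 defines the interim weeks, section 11.4 refers to each study visit and to out-of-range frequency tables, and the shells are visibly abbreviated, naming only 12-week columns. This stands in part: much of the problem is a conflict between SAP text and shells, not a decision to ignore on-treatment data. But the SAP's own PSP shell prints interim on-treatment and mid-treatment visits, whereas the laboratory shells do not. The text also leaves days 2–14 unassigned and does not state the patient-level shift count.

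A reader might infer more than the documents support:

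- **That such elevations vanish from every planned output, or that day 2–14 samples are lost.** They do not. SAP 11.4 keeps the values in listings. Protocol 11.1 counts an abnormal laboratory finding as a possible AE, and SAP 11.2 tabulates treatment-emergent AEs. Only the laboratory summary tables are affected.
- **That ALT elevations are early.** Week 1 timing is given for bilirubin only. ALT is at risk mainly because the Week 4–16 rows are missing.
- **That hemoglobin falls would disappear by EoT.** Neither document says hemoglobin recovers on treatment.

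Two further limits stand. Testing follows routine practice and the study flowchart is not shown, so the number of day 2–14 samples is unknown. The SAP also cites Protocol version 4.0 of July 2017, while the supplied protocol is version 3.0 (country version 1.0, 2015), so departure from the governing 9.7.4 cannot be confirmed. The mismatch between SAP text and shells, and the window gap, rest on the SAP alone.

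**Conclusion.** The point holds for the laboratory summary tables. Following the shells leaves 54 of 84 on-treatment days (12 weeks) or 138 of 168 (24 weeks) without a table row. The during-treatment shift count in the supplied protocol is not delivered, and SAP 16 does not declare the omission. Bilirubin and ALT elevations that resolve before the EoT sample can therefore be missing from these summaries.

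This assumes that the shells are programmed as drawn and that patients complete the planned course. How many patients would be affected cannot be estimated from the documents. The primary endpoint is untouched.

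**What to change.** 1. Add a table by regimen group giving the number and percentage of patients with any on-treatment shift from baseline by reference range (low, normal, high), with the worst on-treatment value as a summary: highest for ALT, AST and bilirubin, lowest for hemoglobin and platelets. Use all on-treatment values regardless of window. The shift count supplies what Protocol 9.7.4 asks for; the worst value is an addition. This table captures a Week 1 bilirubin peak if it was sampled, and also covers the day 127–139 gap.
2. Add the already defined Week 4, 8, 12 and 16 rows to Tables 4.5.1–4.6.X, so that the shells match SAP 5.2 and 11.4.
3. Assign days 2–14 to an early on-treatment window.

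The cost is a few extra descriptive tables from data already collected; no endpoint or sample size changes. The early window may hold few samples, so show the number of patients contributing to it.
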